#### 8.1 Adverse Event Categorization

The Investigator will be required to rate the likelihood of an event being device-related (Possible, Probable, Highly Probable) or non-device-related (unlikely, definitely not) in their AE evaluation.

## 8.2 Adverse Event Reporting

On finding an AE the Investigator will complete an Adverse Event form (AE form) in EDC to capture the event.

The Investigator must notify Visioncare Research of the AE, so that they are able to provide advice and support to the Investigator on how to proceed.

The Investigator must do this by providing the information on the AE eCRF as soon as possible as and no later than:

- 24 hours from discovery if event is Serious or Significant
- 5 working days from discovery if event is Non-Significant

Once the form is saved, an automatic email will be sent to VCR and the Sponsor to notify them of the event. If the AE form in EDC cannot be completed on the day of discovery of the AE, then the Medical Monitor must be contacted to notify them of the AE.

If applicable, VCR will advise the Investigator to notify the IRB as per the IRB requirements. VCR may notify the IRB on behalf of the Investigator.

The Investigator must notify VCR in writing that the AE has been reported to the IRB.

## 8.3 Adverse Event Documentation

Investigators are required to document and follow-up all AEs.

All AEs must be documented on an AE form in EDC upon event discovery. For all ocular AEs, one AE form is used per eye. For AEs which are non-ocular only one AE form will need to be completed in EDC per AE.

### **Procedure:**

The Investigator has the responsibility to:

1. Complete as much information as possible on the AE form in EDC upon event discovery. This includes:
  - A detailed description of the AE and a diagnosis, including a probable cause.
  - Likelihood of the AE being device-related
  - Lens lot and power details (irrespective of whether lenses were being worn at time of the AE)
2. Include in the patient notes detailed drawings that detail size, location and depth or photographs (if necessary)
3. If serious, collect any contact lenses worn, solutions, and the lens case used at the time.
4. Report the AE to the sponsor (via VCR) and the IRB within the specified timelines (see Adverse Event Reporting section 8.2).
5. Follow study subject until resolution recording all information on an unscheduled visit eCRF, including VA, symptoms, slit lamp findings, resolution, and permanent sequelae if any.
6. Complete all remaining information as required on the AE resolution eCRF. If follow-up of the AE is required, the resolution form can only be completed when all AE follow-up visits are finished. The following additional information will also be completed on the AE resolution form:
  - Outcome, ocular sequelae if any

- Whether the patient is discontinued from the study as a result of the AE

#### 8.4 Adverse Event Follow-up

The Investigator will conduct follow-up examinations until the condition:

- Has returned to pre-event status,
- Is considered stabilized
- Or has been satisfactorily explained.

If the subject is referred for medical attention, they will be tracked by the Investigator until the aforementioned conditions are met.

Follow-up data will be collected on an unscheduled visit eCRF and on the AE form in EDC.

The Investigator should use his/her clinical judgement as to whether or not the subject reporting with an AE should continue in the study.

##### 8.4.1 Device Deficiency

A device deficiency means the failure of the device to meet its performance specification or otherwise perform as intended. A device deficiency would be considered reportable to the Sponsor if considered to be likely to cause or contribute to a Serious Adverse Event.

The Investigator will be required to report all reportable device deficiencies to the VCR/Sponsor via the applicable form in the EDC system.

##### 8.4.2 Sponsor Safety Responsibilities

The sponsor will ensure that all participating Investigators are promptly informed of significant new safety information with respect to the study devices as per regulatory requirements.

To comply with this, the sponsor is responsible for promptly advising (in writing, via VCR) all Investigators conducting clinical studies of any incidents of serious or unexpected adverse events/unanticipated adverse device effects reported for the devices/products involved in those studies.

#### 8.5 Study Completion

The study is completed when all subjects have completed the final visit (Visit 3 or 5 depending on control lens group) or been discontinued, and have been exited from the study.

### **9 DATA MANAGEMENT**

---

#### 9.1 Electronic Case Report Forms/Data Collection

The clinical data for this study will be entered by designated study site personnel onto electronic report forms (eCRFs) using the electronic data collection (EDC) system Medrio.

Medrio is compliant with all relevant aspects of ICH/Good Clinical Practices and 21 CFR Part 11 (Electronic Records & Electronic Signatures) regulations.

9.2 Data Quality Assurance

When eCRFs are reviewed at VCR, they will be subjected to error checking and data queries will be raised electronically via the EDC system for resolution of omissions and discrepancies by the investigator.

Before the final closing of the database, the data will be checked and approved for analysis as per VCR SOPs. This includes checking for missing or erroneous data entries.

9.3 Data Entry and Storage

All study data shall be entered into the study eCRFs. All statistical analyses will be completed by VCR using SAS software (SAS Institute Inc., Version 9.4 or later).

## 10 SAMPLE SIZE AND STATISTICAL METHODS

10.1 Sample Size Rationale

Assuming a discontinuation rate of 10%, 100 subjects, 50 subjects per group would detect a mean difference in comfort of smaller than 1.0 (0-10 scale).

**Table 4: Sample size calculation.**

| Comfort  |      |      |      |
|--|------|------|------|
| Scale  | 0-10 |      |      |
| Type I (a)                                       | 5%   |      |      |
| Power (1-b)                                      | 80%  |      |      |
| SD of difference between pairs ( $\sigma$ )      | 1.9  |      |      |
| Minimum detectable difference (T-C) ( $\delta$ ) | 0.50 | 0.75 | 1.00 |
| Minimum size per group (Inequality)              | 116  | 53   | 31   |

N.B. Calculations performed using Hintze, J. (2013). PASS 12. NCSS, LLC. Kaysville, Utah, USA. [www.ncss.com](http://www.ncss.com).

10.2 End-points

**Primary:**

Comfort reported at visit. Subjects will be asked the following question: "Thinking about the last week of CL wear, how would you assess the overall comfort of your/the study lenses – please rate overall comfort on a 0 to 10 scale, where 10= 'can't feel the lenses' and 0= 'extremely uncomfortable' "

**Secondary:**

The following variables will be the secondary end-points:

- i. Wearing time: Average WT & Comfortable WT [hrs]
- ii. Surface wetting: Pre-lens tear film quality [0-4]
- iii. Deposits: Film deposits [0-4]
- iv. White spot deposits [no.]

## v. Overall lens fit acceptance [0-4].

10.3 Statistical Considerations

All statistical analyses will be performed using the SAS software Version 9.4 or later (SAS Institute, Cary, NC).

The final analysis will be completed after all subjects have been exited from the study, all queries have been resolved, and the database has been locked.

The overall type I error rate will be preserved at 5%. All tests will be two-sided. The primary hypothesis must be met in order to satisfy the objective of this study.

From the insertion and removal times the average wearing time will be calculated. If the subject indicates that lens comfort deteriorates during wear, the comfortable wearing time will be calculated from the insertion time and the time that lenses become uncomfortable. If there is no deterioration in comfort then the average wearing time will be used [REDACTED]

Data from unscheduled visits will not be included in the analysis.

Any deviations from this analysis plan will be detailed in the study report.

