## 2 STUDY OBJECTIVES

---

The aim of this study will be to evaluate the comparative clinical performance of the Avaira Vitality™ silicone hydrogel lens used in daily wear and to compare this with competitive hydrogel lens products, Biomedics 55 Premier and Acuvue 2.

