### 3.3 Primary Outcome Hypothesis

Subjective comfort reported at the visit will be better with Avaira Vitality than the control contact lenses at the final visit.

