### 3.4 Secondary Outcome Hypotheses

- i. Average wearing time will be longer with Avaira Vitality than the control contact lenses at the final visit.
- ii. Comfortable wearing time will be longer with Avaira Vitality than the control contact lenses at the final visit.
- iii. Pre-lens tear film quality will be better with Avaira Vitality than the control contact lenses at the final visit.
- iv. Film deposits will be better with Avaira Vitality than the control contact lenses at the final visit.
- v. White spot deposits will be fewer with Avaira Vitality than the control contact lenses at the final visit.
- vi. Overall lens fit acceptance will be better with Avaira Vitality than the control contact lenses at the final visit.

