10.8 Secondary Statistical Analysis

The secondary variables will be analysed using mixed linear models. The models will include the following fixed effects: lens type, control group, site, and the interaction of lens type by control group; and subject nested in site as a random effect. The least-square means and their differences will be reported with 95% confidence intervals for each lens type by control group. Conclusions will be drawn from the 95% confidence interval of the least-square mean differences.

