10.9 Additional Statistical Analysis

Other selected variables may be analysed using appropriate statistical methods. A *P*-value less than or equal to 0.050 will be regarded as statistically significant.

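### Section 10.3 promises an overall 5% type I error rate that no procedure delivers for the secondary hypotheses, and no section says which comfort contrast(s) decide the primary

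*Combined protocol and SAP*

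**What the plan says.** Section 10.3 makes two statements together. The first is the error-rate commitment, "The overall type I error rate will be preserved at 5%. All tests will be two-sided". The second defines success: "The primary hypothesis must be met in order to satisfy the objective of this study".

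The primary hypothesis in 3.3 is directional and names the controls in the plural: "Subjective comfort reported at the visit will be better with Avaira Vitality than the control contact lenses at the final visit". Section 2 gives the aim as "to compare this with competitive hydrogel lens products, Biomedics 55 Premier and Acuvue 2". Section 10.7 fits lens type, control group, site and the lens-by-control-group interaction. It reports the comfort differences by control group, so there are two comfort contrasts.

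Section 3.4 lists six secondary hypotheses, all directional, for example "Average wearing time will be longer with Avaira Vitality than the control contact lenses at the final visit". Section 10.8 treats them as 10.7 treats the primary: "The least-square means and their differences will be reported with 95% confidence intervals for each lens type by control group", followed by "Conclusions will be drawn from the 95% confidence interval of the least-square mean differences". For other variables, 10.9 says that a P-value "less than or equal to 0.050 will be regarded as statistically significant".

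**The concern.** There are two gaps.

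**Secondary hypotheses.** The 5% statement carries no qualification, yet nothing in the statistical section produces it beyond the primary. The secondary analyses use the same decision language as the primary, and nothing labels them descriptive. A chance secondary finding could therefore be reported as a conclusion under an error rate that does not cover it. Section 3.4 also leaves open whether each secondary hypothesis must hold against each control.

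**Primary hypothesis.** The study objective depends on the primary being met, but the plan does not say what meeting it requires when there are two contrasts. If the test lens beats one control and not the other, the plan gives no answer. The choice could be made with results in view: wear order is fixed (3.7), so visit identifies the lens within a control group, and investigators are unmasked (3.6).

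**Working it through.** **Inputs from the plan.** SD of paired differences 1.9, two-sided alpha 5%, power 80% (Table 4); 10% discontinuation (10.1); 50 to 60 subjects per control group (4.3). Evaluable per group: 50 × 0.9 = 45 and 60 × 0.9 = 54.

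**Assumptions not in the plan.** Correlations between secondary variables, because none are given. The two control groups are independent, since they contain different subjects. Power comes from a paired t-test within each group, as a close stand-in for the mixed-model contrast.

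**Step 1: reproduce Table 4.** The paired t-test (noncentral t) gives 116, 53 and 31 for differences of 0.50, 0.75 and 1.00, an exact match. Table 4 therefore sizes one within-group contrast at the full 5%.

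**Step 2: secondary error rate, each control judged separately.** 6 variables × 2 groups = 12 contrasts. A 95% interval gives a false 'better' with probability 0.025 and a false difference in either direction with probability 0.05. Under independence:
- at least one false 'better': 1 − 0.975^12 = 0.262
- at least one false difference: 1 − 0.95^12 = 0.460

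With an exchangeable correlation ρ within each group (normal model, numerical integration):

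| ρ | false 'better' | any false difference |
|---|---|---|
| 0 | 26.2% | 46.0% |
| 0.3 | 22.8% | 42.4% |
| 0.5 | 19.7% | 37.2% |
| 0.8 | 13.4% | 25.8% |

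If only the two wearing-time variables correlate, at 0.5 to 1.0, false 'better' is 25.6% to 22.4%.

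**Step 3: secondary error rate if both controls must succeed.** With all nulls true: 1 − (1 − 0.025²)^6 = 0.0037, about 0.4%. If the lens truly beats one control on every variable and equals the other, the rate can reach 1 − 0.975^6 = 0.141, or 10.4% to 6.9% at ρ of 0.5 to 0.8. So even this rule does not guarantee 5%.

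**Step 4: primary error rate, no period effect.**
- Both required: at most 0.025
- Either suffices: 1 − 0.975² = 0.0494

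**Step 5: how often the two comfort contrasts disagree.** Let p be the power of one contrast and let the true difference be the same in both groups. Exactly one succeeds with probability 2p(1 − p); both succeed with probability p².

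| Evaluable per group | True difference | p | Exactly one | Both |
|---|---|---|---|---|
| 45 | 0.75 | 0.736 | 38.9% | 54.1% |
| 45 | 1.00 | 0.932 | 12.6% | 86.9% |
| 54 | 0.75 | 0.813 | 30% | 66.0% |
| 54 | 1.00 | 0.967 | 6.4% | 93.5% |

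Joint power of 80% is reached at a difference of 0.93 (45 per group) or 0.85 (54).

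**The case against.** **The 5% may have been meant for the primary alone.** The commitment sits beside the sentence that ties the objective to the primary, and no secondary result can satisfy that objective. This is a fair reading and would reduce the first gap to a missing label. But the text does not limit the statement, and 10.8 uses the same decision wording as 10.7.

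**The primary might serve as a gate.** It is written as the condition for satisfying the objective, not as a condition for testing the secondaries. Even as a gate, it would not control error among the six.

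**46% overstates the problem.** This stands. All six hypotheses are directional, so a result against the test lens cannot support one of them. Independence is also implausible for the wearing-time pair, since 10.3 sets comfortable wearing time equal to average wearing time when comfort does not deteriorate. The figures comparable with the primary are 26% to 13%.

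**A reader might infer that the primary error rate is inflated, to 9.75% (1 − 0.95²).** That counts findings in both directions under an 'either' rule. The hypothesis is directional and the plan states no 'either' rule; a false 'better' is 4.9% even then. However, Step 4 holds only without a period effect. Wear order is fixed (3.7) and 3.2 concedes possible sequence bias. As an illustration with an assumed drift of 0.3 points towards the second lens, no lens effect and 45 per group, false 'better' is 18% per contrast, 3% under 'both' and 32% under 'either'. That is a design limitation that no multiplicity rule cures. Step 2 carries the same condition.

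**A single pooled lens effect might be intended.** Reporting by control group in 10.7 and per-group sizing in 10.1 give that little support.

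**Conclusion.** The concern holds in two limited parts.

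First, the plan states an overall 5% rate and provides nothing to deliver it for the secondary hypotheses. With each control judged separately and all lens and period effects null, the chance of at least one false 'better' is 26% under independence and 23% to 13% at the assumed correlations. Any false difference is 46%, and 42% to 26%.

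Second, the success rule for the primary is not stated. The wording of 3.3 and section 2 and the sizing in 10.1 fit 'both controls' best, but a split result is a realistic outcome: 39% or 30% at a true difference of 0.75.

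The documents do not show that the primary's error rate exceeds 5% through multiplicity, or that the sample size is wrong. The plan should be corrected, but the primary analysis is not invalidated.

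**What to change.** **1. Secondary hypotheses.** In 10.3, limit the 5% statement to the primary hypothesis. In 10.8, replace the sentence on drawing conclusions with: 'Secondary confidence intervals are supportive and are not controlled for multiplicity.' If confirmatory secondary claims are wanted, test them only after the primary succeeds, use Holm or a fixed order, and state whether each needs both controls.

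**2. Primary hypothesis.** In 10.3 and 10.7, state: 'The primary hypothesis is met only if the 95% confidence interval for Avaira Vitality minus control lies entirely above 0 in both control groups.' No alpha split is needed. Fix this before any outcome data by lens are reviewed; database lock is too late, because lens identity is visible as data accrue.

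**Cost.** Wording only, with no extra subjects or procedures. Fewer secondary results can be presented as confirmed. Requiring both controls lowers power at a difference of 0.75 from 74% to 54% (45 per group) or from 81% to 66% (54). The claim in 10.1 of detecting a difference below 1.0 still holds, since 80% joint power is reached at 0.93 or 0.85.

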### 3.5 Safety Hypothesis

The study lenses are FDA approved, therefore, no safety end points are required.

However, in order to ensure the continued safety of the subjects in the trial, slit lamp findings will be assessed at all visits and the spectacle refraction and VA will be collected at the start and end of the study. Adverse events will also be recorded and monitored following the procedures listed in Section 8.

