#### 7.4 Subject Discontinuation

Subjects may be discontinued from the study in the event of any of the following occurring:

- i. Unacceptable subjective discomfort (i.e. lens cannot be tolerated or worn)  
[REDACTED]
- ii. Unacceptable fit (i.e. lens too tight or too loose)
- iii. At the discretion of the Investigator or the subject

In the event of discontinuation, the Study Exit eCRF must be completed and the study exit date recorded on the Source Document Record. The Investigator will indicate the primary reason for discontinuation by selecting one of the boxes provided on the Exit eCRF. Comments can be added to the eCRF if necessary.

If a subject is discontinued outside of a visit window, an Unscheduled Visit eCRF must also be completed

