10.4 Analysis Population

Statistical analyses will be conducted on all randomized subjects who have successfully completed the study without a protocol deviation that is regarded as impacting the assessment of the primary hypothesis (as per protocol). Missing data will be excluded from the analysis and will not be extrapolated from the collected data.

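### Section 10 defines no safety set, and neither its completers-only population nor its unscheduled-visit exclusion exempts safety data (minor)

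*Combined protocol and SAP*

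**What the plan says.** Section 10.4 (Analysis Population): "Statistical analyses will be conducted on all randomized subjects who have successfully completed the study without a protocol deviation" of a kind that affects the primary hypothesis. No other population appears in the visible text of Section 10. The same section adds: "Missing data will be excluded from the analysis and will not be extrapolated from the collected data".

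Section 10.3 (Statistical Considerations): "Data from unscheduled visits will not be included in the analysis". The sentence is not limited to particular variables.

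Section 10.5 promises descriptive statistics at dispensing and at each follow-up visit, by control group and lens type. It does not restrict them to the end-points listed in 10.2.

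Section 3.5 says no safety end-points are needed because the lenses are FDA approved. To protect subjects, "slit lamp findings will be assessed at all visits", refraction and VA are taken at the start and end, and AEs are recorded under Section 8.

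Section 8 says where safety data go:
- Section 8.3 requires every AE to be entered on an AE form, with a later AE resolution form. Item 5 of its procedure reads: "Follow study subject until resolution recording all information on an unscheduled visit eCRF, including VA, symptoms, slit lamp findings".
- Section 8.4 puts follow-up data on the unscheduled-visit form and also on the AE form.

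Section 7.4 adds: "If a subject is discontinued outside of a visit window, an Unscheduled Visit eCRF must also be completed".

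**The concern.** The protocol collects slit-lamp findings, VA and AEs to watch over subjects. The introduction to Section 8 says ocular AEs and related non-ocular AEs will be reported, and that recurring device-related events are usually tabulated separately. It names no population, denominator or rule for attributing events to a lens. The only rules a programmer would find are those in 10.3 and 10.4, which were evidently written with comfort and lens performance in mind.

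Applied to safety data, those rules select on the wrong thing. Someone who stops because of an event has not successfully completed the study and so leaves the set. Because the control lens always comes first (3.7), a subject who stops in the first period never wears the test lens, and one who stops on the test lens is dropped from the summaries of both lenses. What is at stake is whether the report's safety tables describe everyone who wore each lens or only those who finished.

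**Working it through.** The plan gives no figure for this point. Table 4 concerns comfort only and is unaffected, so the check is mainly a comparison of passages.

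**Step 1. Trace each kind of safety data through the two rules, read literally.**

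| Data | Where recorded | Effect of 10.3 | Effect of 10.4 |
|---|---|---|---|
| AE description, relatedness, lens details, outcome | AE form and AE resolution form (8.3) | None | Left out if the subject is outside the completer set |
| Scheduled slit-lamp findings; start and end VA | Scheduled-visit and exit forms (some fields blacked out) | None | Left out if the subject is outside the set |
| Slit lamp, VA and symptoms at AE follow-up | Unscheduled-visit form (8.3 item 5; 8.4, which also names the AE form) | Unscheduled-form data left out, for completers too | Left out if the subject is outside the set |
| Examination at a discontinuation outside a window | Unscheduled-visit form (7.4) | Left out | Left out; the subject is not a completer |

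So 10.3 removes examination data but not event records. Only 10.4 can change an AE count.

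**Step 2. Are unscheduled examinations incidental?** No.
- Section 4.9 requires an unscheduled evaluation before wear resumes after any AE that suspended it.
- Section 7.2.1 allows a scheduled follow-up only when the subject attends in study lenses.
- Section 7.5 makes presenting VA, slit lamp and symptoms compulsory at unscheduled visits.

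Eyes with a problem are therefore directed to the visits that 10.3 leaves out.

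**Step 3. How many subjects does the completer set omit?** Inputs are the 10% discontinuation assumption (10.1) and approximately 100-120 subjects (4.3).
- 100 × 0.10 = 10 omitted, 90 kept.
- 120 × 0.10 = 12 omitted, 108 kept.

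Exclusions for protocol deviations would come on top.

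**Step 4. Which way would an AE proportion move?** Let d be the overall share of subjects discontinuing and s the share of event subjects who discontinue. With N subjects and true event proportion p, the completer table shows N·p·(1 − s) / [N·(1 − d)]. Its ratio to p is (1 − s)/(1 − d), whatever the event rate. With d = 0.10 and no deviation exclusions:
- s = 0: 1/0.9 = 1.11, overstated
- s = 0.10: 0.9/0.9 = 1.00, unchanged
- s = 1: 0/0.9 = 0, every event subject missing

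The proportion is understated only if event subjects leave more often than subjects overall. The documents do not give s, so neither size nor direction can be fixed.

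**The case against.** The strongest reply is that no planned safety summary exists to be distorted. Section 3.5 sets no safety end-point, and Sections 10.2 and 10.5 to 10.9 specify no AE or slit-lamp table. The population in 10.4 is framed around the primary hypothesis, and the 10.3 sentence follows the derivation of wearing time, so both can be read as covering only comfort and the secondary variables. Section 8 has its own reporting commitment and counting rules, 7.1 requires all enrolled subjects to be accounted for, and 7.2.8 requires an exit form for every consented subject.

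Much of this stands. A reader might infer that the plan discards the adverse events themselves. It does not: every event has its own AE and resolution forms, which 10.3 does not touch. A reader might also infer that safety results must be biased towards no events. That does not follow either: 8.4 leaves continuation after an AE to the investigator's judgement, 4.9 provides for return to wear after resolution, and Step 4 shows that the direction can reverse.

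What does not stand is that the narrower reading settles the matter. It is an inference. The text says statistical analyses and the analysis without qualification, and 10.5 is broad enough to take in slit-lamp findings. Having no safety end-point removes a hypothesis test. It does not supply a denominator for events that the protocol says it will report.

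**Conclusion.** The point holds as a minor gap in the analysis plan. Section 10 defines one completers-only population and one blanket exclusion of unscheduled-visit data, with no safety exemption in either. Taken literally, discontinued subjects drop out of any slit-lamp, VA or AE summary made under Section 10, and event-related examinations recorded at unscheduled visits drop out of the slit-lamp and VA summaries even for completers.

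The size that can be stated is the number of subjects omitted: about 10 of 100 or 12 of 120 at the plan's 10% discontinuation, before deviation exclusions. The effect on any event proportion cannot be stated, because the share of event subjects who discontinue is not given.

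It would go too far to say that the trial could not yield a valid event rate per lens. The AE form takes lens lot and power (8.3), and the Source Document Record holds the lenses worn and the exit date (11.5). The information is collected; the reporting rule is what is missing. The conclusion rests on the literal wording and the visible text of Section 10. The comfort analysis and its sample size are not affected.

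**What to change.** 1. In 10.4, add a safety set: every subject in whom a study lens was inserted or dispensed, regardless of completion or protocol deviation.
2. State that AEs, device deficiencies, slit-lamp findings and VA are summarised descriptively on that set, by lens worn at onset or at examination, with the number of subjects exposed to each lens as denominator. If exposure time is wanted, use calendar time from dispensing to lens change or exit. Hours of wear would not be fully available, since Table 2 shows no wearing-time collection at unscheduled or exit visits.
3. In 10.3, limit the exclusion of unscheduled-visit data to the primary and secondary end-point analyses, and say that these data are used in the safety summaries.

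The cost is a few sentences in Section 10 and a few more descriptive tables. The AE, unscheduled-visit and exit forms already exist, so no extra subjects, visits or data collection are needed. The change is best made before database lock.
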